#### 10. ADVERSE EVENTS

#### 10.1. Definition of Adverse Event

An adverse event is any untoward medical occurrence that may appear or worsen in a patient during the course of a study. It may be a new intercurrent illness, a worsening concomitant illness, an injury, or any concomitant impairment of the patient's health, including laboratory test values, regardless of etiology. Any worsening (i.e., any clinically significant adverse change in the frequency or intensity of a pre-existing condition) should be considered an adverse event. A diagnosis or syndrome should be recorded on the adverse event page of the eCRF rather than the individual signs or symptoms of the diagnosis or syndrome. A worsening of the condition under study, alopecia areata, will not be reported as an adverse event.

All patients will be monitored for adverse events during the study. Assessments may include monitoring of the following parameters: the patient's clinical symptoms, laboratory, physical examination findings, or findings from other tests and/or procedures.

An adverse event reported after informed consent, but before the first dose of study drug (i.e., Day 1), will be considered a pretreatment adverse event and will be captured on the eCRF. Adverse events will be considered treatment-emergent if the onset is after the first dose of study drug or if an ongoing Adverse Event worsens after dosing is initiated.

Laboratory results deemed Abnormal and clinically significant by the investigator will be recorded as an adverse event in the eCRF and should be fully investigated and repeated for verification.

Regardless of severity grade, only laboratory abnormalities that fulfill a seriousness criterion need to be documented as a serious adverse event.

If a laboratory abnormality is one component of a diagnosis or syndrome, then only the diagnosis or syndrome should be recorded on the adverse event eCRF. If the abnormality was not a part of a diagnosis or syndrome, then the laboratory abnormality should be recorded as the adverse event. If possible, the laboratory abnormality should be recorded as a medical term and not simply as an abnormal laboratory result (e.g., record thrombocytopenia rather than decreased platelets).

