#### **Adverse Events**

An adverse event reported after informed consent, but before the first dose of study drug (i.e., Day 1), will be considered a pre-treatment adverse event. Treatment-emergent adverse events (TEAEs) will be defined as any adverse event that occurs after administration of the first dose of study drug until Week 24 or the Early Termination Visit. The number and percentage of patients who report TEAEs will be summarized by system organ class and preferred term.

Treatment emergent adverse events will also be summarized by intensity as well as relationship to study drug.

Patients who report the same preferred term on multiple occasions will be counted once for the preferred term: under the highest severity when summarized by severity and under the closest relationship to study drug when summarized by relationship. If a patient reports multiple preferred terms for a system organ class, the patient will be counted only once for that system organ class.

The number and percentage of patients who experience TEAEs will be summarized by dosing regimen for the following:

- By system organ class and preferred term
- By severity/intensity, system organ class, and preferred term
- By relationship to study drug, system organ class, and preferred term
- Serious adverse events by system organ class and preferred term
- Serious adverse events by relationship to study drug, system organ class, and preferred term
- Adverse events resulting in discontinuation of study drug by system organ class and preferred term
- Adverse events that result in study drug dose interruption by system organ class and preferred term

By-patient listings will be provided for any deaths, serious adverse events, and adverse events leading to discontinuation of treatment.

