3.4 Changes to the Analysis from the Protocol

The Efficacy analysis population described in the synopsis of the protocol is referred to as the modified Intent-to-Treat (mITT) analysis population in Section 11.3 of the protocol. To avoid confusion, this analysis population will be called the mITT analysis population in this SAP as well as in the statistical outputs.

As per Section 11.4.3 of the protocol, the total number of days on study drug will exclude dose interruptions. However, dose interruptions will not be excluded from the duration of exposure to the study drug as specified in Section 11, in order to be in line with industry's standards.

	STATISTICAL ANALYSIS PLAN, Final v1.0
Protocol Number CP543.2003	Sponsor: Concert Pharmaceuticals, Inc.

As per Section 11.4.4 of the protocol, treatment-emergent AEs (TEAEs) are defined as any AE that occurs after administration of the first dose of study drug until Week 24 or Early Termination Visit. However, TEAEs will be defined as any AEs with onset date/time on or after the first dose of study drug (refer to Section 13.1), in order to be in line with the industry's standards.

As per Section 11.4.4 of the protocol, the number and percentage of patients with abnormal, clinically significant laboratory values (per Investigator judgment) will be summarized by dosing regimen for each clinical laboratory variable. This summary has been replaced by shift tables from Baseline to the worst post-Baseline result describing shifts to abnormality as assessed by the central laboratory (low, normal, high) (refer to Section 13.2). Abnormal, clinically significant laboratory values (per Investigator judgement) will be identified in by-patient data listing.

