13.1 Adverse Events

AEs will be coded according to the MedDRA, version 22.0.

An AE reported after informed consent, but before the first dose of study drug (i.e., Day 1), will be considered a pre-treatment adverse event.

TEAEs are defined as any AEs with onset date/time on or after the first dose of study drug. See Appendix 3 for handling of completely or partially missing dates for AEs. In the case where it is not possible to define an AE as treatment emergent or not, the AE will be classified as treatment emergent.

An overall summary table of AEs will be provided. The frequency and percentage of patients who experienced at least one AE, TEAE, TEAE by greatest relationship with study drug, TEAE by highest severity/intensity, serious TEAE, treatment-related serious TEAE, TEAE leading to study drug discontinuation, TEAE leading to study drug dose interruption, TEAE leading to study discontinuation, and TEAE leading to death will be presented.

Frequency and percentage of patients who experienced TEAE will be summarized by SOC and PT. A patient experiencing multiple TEAEs within the same SOC will be counted only once for that SOC. Similarly, a patient experiencing multiple TEAEs within the same PT will be counted only once for that PT. TEAEs will be sorted alphabetically by SOC and PT will be presented by decreasing order of total frequency within each SOC. Serious TEAEs and treatment-related serious TEAEs will be summarized similarly.

Frequency and percentage of patients who experienced TEAE will be further broken down by greatest relationship to study drug. A treatment-related AE is defined as any TEAE that is assessed by the Investigator as definitely, probably or possibly related to study drug. A not related TEAE is defined as any TEAE that is assessed by the Investigator as unlikely related or not related to the study drug. TEAE with an unknown/missing relationship to study drug will be considered as treatment related. A patient experiencing multiple TEAEs within the same SOC will be counted only once for that SOC under the greatest relationship to study drug. Similarly, a patient

	STATISTICAL ANALYSIS PLAN, Final v1.0			
Protocol Number CP543.2003	Sponsor: Concert Pharmaceuticals, Inc.			

experiencing multiple TEAEs within the same PT will be counted only once for that PT under the greatest relationship to study drug.

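### SAP 13.1 defines TEAEs by onset date alone, so an AE that opens in screening and worsens on drug, treatment-emergent under Protocol 10.1, can fall outside the TEAE summaries

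*SAP*

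**What the plan says.** Four places bear on when an AE is treatment-emergent.

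- **Protocol 10.1** has two limbs. An event qualifies "if the onset is after the first dose of study drug or if an ongoing Adverse Event worsens after dosing is initiated".
- **Protocol 11.4.4**, the analysis section, has one limb with an end point: "any adverse event that occurs after administration of the first dose of study drug until Week 24 or the Early Termination Visit". It does not mention worsening.
- **SAP 3.4** cites the 11.4.4 definition and replaces it: "TEAEs will be defined as any AEs with onset date/time on or after the first dose of study drug". The stated reason is industry practice. It does not refer to Protocol 10.1.
- **SAP 13.1** repeats the onset rule: "TEAEs are defined as any AEs with onset date/time on or after the first dose of study drug". The paragraph before it says: "An AE reported after informed consent, but before the first dose of study drug (i.e., Day 1), will be considered a pre-treatment adverse event". Neither sentence has an exception for an event that later worsens on drug.

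On recording, Protocol 10.5 collects AEs from consent and asks for a separate entry for each one, and Protocol 10.2.4 asks for start and stop dates. Protocol 10.1 adds: "Any worsening (i.e., any clinically significant adverse change in the frequency or intensity of a pre-existing condition) should be considered an adverse event".

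**The concern.** AEs are recorded from consent, and screening can run for up to 28 days, so some patients may reach first dose with an AE already open. Suppose such an event starts as mild, becomes severe on study drug and leads to discontinuation. Under Protocol 10.1 it is treatment-emergent. Under SAP 13.1 its known onset date makes it pre-treatment.

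Tolerability is part of the primary objective. SAP 13.1 tabulates incidence, severity, relatedness, dose interruption and discontinuation on TEAEs, and its two discontinuation listings are also limited to TEAEs. Protocol 11.4.4 promises a listing of AEs leading to discontinuation of treatment without that limit. SAP Section 1 undertakes to document changes from the protocol's planned analyses, yet a reader of SAP 3.4 would not learn that the worsening limb of 10.1 is not applied.

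**Working it through.** The plan gives no figure to reproduce here. The check is a comparison of definitions, followed by one scale calculation.

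**Step 1. Classify the same event under each definition.** Take an AE with a known onset in screening that is still open at first dose, worsens on drug, and is kept by the site as one record with its original start date.

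| Source | Rule | Treatment-emergent? |
|---|---|---|
| Protocol 10.1 | Onset after first dose, or an ongoing AE worsens | Yes |
| Protocol 11.4.4 | Occurs after first dose, up to Week 24 or early termination | Not by its wording; worsening is not mentioned |
| SAP 3.4 | Onset on or after first dose | No |
| SAP 13.1 | Onset on or after first dose; AEs reported before dosing are pre-treatment | No |

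The protocol is therefore inconsistent with itself, and the SAP follows the narrower of its two definitions on this point. SAP 3.4 does widen capture in another respect, because it removes the Week 24 or early-termination cut-off.

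**Step 2. Look for another rule that brings the event back.**

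- SAP 13.1 defaults to treatment-emergent only when status cannot be determined. A known pre-dose onset can be classified, so the default does not apply.
- SAP Appendix 3 imputes missing or partial dates. It leaves a complete pre-dose date unchanged.
- No passage requires a second record, with its own onset date, when an AE already open at first dose gets worse.

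**Step 3. Trace where the event would and would not appear.**

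- Left out: TEAE incidence by system organ class and preferred term; TEAEs by severity and by relationship; serious TEAE tables; TEAE counts for dose interruption and for drug or study discontinuation; and the two TEAE discontinuation listings.
- Still present: the row for patients with at least one AE in the overall summary (SAP 13.1); the listing of all AEs, and those of serious AEs and AEs leading to death where they apply; and the premature-discontinuation counts and reasons in SAP 7.1 if the patient leaves the study.
- Covered separately: a laboratory value that moves to Grade 3 or 4 from a lower baseline is summarised under SAP 13.2, whatever the AE record says.

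**Step 4. Scale.** The planned arm size is about 30 (Protocol 6.3, SAP 3.1). For a patient whose only qualifying event in a given table row is the missed one, the change in that arm's percentage is 1/30 = 0.033, or 3.3 points downward. If the patient has another TEAE in the same row, that row does not change. The documents give no rate of AEs open at first dose or of later worsening, so no total can be calculated.

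**The case against.** The best defence is that Protocol 10.1 makes a clinically significant worsening of a pre-existing condition an AE in its own right, and Protocol 10.5 asks for each AE to be a separate entry. A site reading these together may well open a new record dated from the worsening, and SAP 13.1 would then count it. Entry rules may also sit in the Study Manual or the Data Management Plan, which are not part of these documents. This makes capture plausible but does not secure it. The 10.1 sentence concerns pre-existing conditions, and neither section says what to do with an AE already open on the eCRF. Protocol 10.1 also lists worsening of an ongoing AE as a separate limb, which would add nothing if every such worsening already had a post-dose onset.

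It is also fair to say that the SAP did not originate the omission. A reader might infer that it removed a rule from the protocol's analysis section, but 11.4.4 never contained one, and SAP 3.4 openly declares its change to 11.4.4.

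A reader might further infer that every AE output loses these events, or that the comparison of regimens is biased in a known direction. The documents support neither. Several outputs do not depend on TEAE status, both arms are randomised, blinded and handled by the same rule, and safety is descriptive only. The pool is also limited by the short screening period and the eligibility recheck on Day 1.

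**Conclusion.** The inconsistency is real. Protocol 10.1 counts on-treatment worsening of an ongoing AE; Protocol 11.4.4 and SAP 13.1 do not; and SAP 3.4 does not acknowledge the difference from 10.1. As written, the rule can misclassify such an event, on the condition that the site keeps the original record rather than opening a new one.

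The consequence is confined to the TEAE summaries and TEAE-based discontinuation listings. Within an arm the error can only lower the percentage, by about 3.3 points for each patient who drops out of a row, assuming about 30 treated patients in the arm. The number affected is not stated and is probably small; that is a judgement, not a figure from the documents. No loss of events has been demonstrated. The point is worth correcting because tolerability is part of the primary objective and the change costs almost nothing.

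**What to change.** 1. In SAP 13.1, define TEAEs as AEs with onset on or after first dose, or with onset before first dose that worsen in severity or become serious on or after first dose.
2. Amend the neighbouring pre-treatment sentence so that it excludes events that meet the second limb.
3. In SAP 3.4, record that this definition follows Protocol 10.1 and reconciles it with 11.4.4.
4. In the eCRF completion guidance, tell sites to enter a worsening of an AE open at first dose with its own start date, so that the rule can be programmed.

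SAP 13.1 already counts each patient once per system organ class and preferred term, so a second record would not inflate the TEAE incidence tables. The cost is a few sentences in the SAP and one line of site guidance, to be settled before database lock and unblinding. Records already entered would need a check for AEs open at first dose.

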13.2 Clinical Laboratory

Descriptive statistics will be presented by dosing regimen at Baseline and each post-Baseline visit for data related to chemistry, hematology, and lipids tests. Change from Baseline values will also be presented at each post-Baseline visit.

Separate listings will be provided for abnormal (low or high) chemistry (including lipids) and hematology laboratory results. Clinical laboratory results that fall outside the central laboratory reference range will be interpreted by the Investigator as Abnormal, not clinically significant (NCS) or Abnormal, clinically significant (CS). Abnormal, NCS and Abnormal, CS laboratory values will be flagged in the by-subject data listings.

Additionally, treatment-emergent potentially clinically significant (PCS) laboratory values will be identified. Potentially clinically significant values are defined as those that meet Grade 3 or Grade 4 toxicity criteria from the common terminology criteria for AEs (CTCAE) criteria. Treatment-emergent PCS laboratory values are those in which the Baseline value is not PCS and the post-Baseline value is PCS. Frequency and percentage of patients with treatment-emergent PCS laboratory values at any time on treatment will be summarized by dosing regimen for each clinical laboratory variable Frequency and percentage of patients with treatment-emergent PCS laboratory values will also be summarized by dosing regimen and post-Baseline visit for each clinical laboratory variable.

Line plots of means (+/- SEM) in laboratory value over time by dosing regimen will be presented for each hematology parameter of interest (i.e., hemoglobin, absolute neutrophils count, platelets, and reticulocytes).

	STATISTICAL ANALYSIS PLAN, Final v1.0
Protocol Number CP543.2003	Sponsor: Concert Pharmaceuticals, Inc.

Separate listings of all data for chemistry, hematology, lipids, serum pregnancy, serology, and other laboratory tests will also be provided. Treatment-emergent PCS laboratory values that result in dose interruption will be identified in these listings.

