#### **Duration of treatment:**

Patients will receive up to 24 weeks of study drug

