5.3 Windowing Conventions

For scheduled visits, there will be no reassignment of the analysis visit based on date, and all data will appear in summary tables based on the nominal timepoint.

Both unscheduled visits and repeat visits will be reassigned to the closest prior visit. If an assessment was already documented at that visit, the scheduled data will be used in summaries. If the scheduled data was missing, then the re-assigned unscheduled visit/repeat visit will be used in summaries.

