5.4 Handling of Repeats, Unscheduled Visits, and Early Termination Data

See Section 5.3 for handling of unscheduled and repeat visits.

	STATISTICAL ANALYSIS PLAN, Final v1.0
Protocol Number CP543.2003	Sponsor: Concert Pharmaceuticals, Inc.

Early termination visit assessments will be summarized as a separate visit.

All data from repeat, unscheduled visits, and early termination visits will be listed.

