6.3 Handling of Dropouts or Missing data

See Appendix 3 for handling of completely or partially missing dates for prior and concomitant medications and AEs. Imputed AE onset and end dates/medication start and stop dates will only be used for the determination of the treatment-emergent/concomitant status. That is, they will not be used to compute any study day or duration and will not be presented in the by-patient data listings.

For the SALT endpoints (e.g., absolute and percent changes from baseline as well as achieving at least 50%, 75%, 80%, and 90% reduction and having a SALT score ≤ 10 and ≤ 20, the Last Observation Carried Forward (LOCF) approach will be implemented for missing SALT score data, e.g., if the SALT score in the Week 16 visit window is missing, the next and closest available ontreatment SALT score measurement before the Week 16 visit window will be used for all remaining SALT assessments: Week 16, Week 20 and Week 24. Missing baseline values will not be carried forward. If a SALT assessment is missing between two non-missing SALT assessments visits, the SALT score at that visit will be interpolated using the mean of the closest pre- and post-assessments.

All other missing efficacy data as well as missing safety data will not be imputed.

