14 APPENDICES

Appendix 1

Table 1 provides a description of the procedures planned at each visit.

	STATISTICAL ANALYSIS PLAN, Final v1.0
Protocol Number CP543.2003	Sponsor: Concert Pharmaceuticals, Inc.

Table 1: Schedule of Events

	Screening	Randomization ¹ Day 1 ² (Visit 2)	Treatment Period					Safety Follow-Up
Event	Day -28 to Day -1 (Visit 1)		Week 2, 6 (Visit 3, 5)	Week 4, 8 (Visit 4, 6)	Week 12 (Visit 7)	Week 16, 20 (Visit 8, 9)	Week 24 ³ /ET (Visit 10)	Week 28 ⁴ (Visit 11)
Informed consent	X							
Eligibility assessment	X	X						
Demographics	X							
Medical and surgical history	X	X						
Randomization		X						
Physical examination	X	X					X	X
Brief physical examination				X	X	X		
Height	X							
Weight	X	X		X	X	X	X	X
Pregnancy test ⁵	X	X	X	X	X	X	X	X
Tuberculosis test ⁶	X							
Clinical laboratory testing ⁷⁸	X ⁹	X	X	X	X	X	X	X
Lipid assessment ¹⁰		X			X		X	X
HBV and HCV test	X							
12-lead electrocardiogram	X	X			X		X	X
Vital signs	X	X		X	X	X	X	X
Severity of Alopecia Tool (SALT) assessment ¹¹	X	X		X	X	X	X	
Photographs ¹²	X	X			X		X	
Patient Satisfaction Questions	X	X		X^{13}	X		X	
Visual Analog Scale (VAS) for Eyebrows		X			X		X	
Clinical Global Impression of Severity	X	X		X^{13}	X		X	
Clinical Global Impression of Improvement				X ¹³	X		X	
Patient Global Impression of Severity	X	X		X^{13}	X		X	
Patient Global Impression of Improvement				X^{13}	X		X	
Study Product Administration at study site		X	X	X	X	X		
Dispense study drug		X		X	X	X		
Study drug accountability				X	X	X	X	
Adverse events ¹⁴	X	X	X	X	X	X	X	X
Concomitant medications ¹⁴	X	X	X	X	X	X	X	X

	STATISTICAL ANALYSIS PLAN, Final v1.0
Protocol Number CP543.2003	Sponsor: Concert Pharmaceuticals, Inc.

ET=Early termination; HBV= hepatitis B virus; HCV = hepatitis C virus; PPD = purified protein derivative.

- Randomization/Day 1 may occur any time after Screening laboratory results are available and reviewed by the Investigator.
- ² All subsequent visits and week increments should be based on the date of Visit 2. All visit windows are ±3 days for subsequent visits.
- ³ Also serves as the Early Termination Visit for patient withdrawal in this period.
- ⁴ The Safety Follow-Up Visit is intended for those patients who do not roll over into an open-label extension and for patients who have been discontinued from the study and completed the Early Termination Visit (Week 24).

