- ⁵ For females of childbearing potential, a serum pregnancy test will be performed at all visits aside from the randomization visit where a urine pregnancy test will be performed.

- 6 If PPD (skin test) is performed, subject will need to return to the clinic 24-48 hours after placement for PPD reading.
- ⁷ Includes hematology and serum chemistry.
- ⁸ When possible, collect pre-dose, except on Visit 11.
- ⁹ Will include thyroid stimulating hormone and hemoglobin A1c at Screening only.
- ¹⁰ Includes total cholesterol, low-density lipoprotein, high-density lipoprotein, and triglycerides.
- ¹¹ Should be performed by the same rater, when possible, for the patient for the duration of the study.
- ¹² For participants who authorize photographs to be taken of their scalp involvement and/or eye and nail involvement.
- ¹³ Will be conducted at Visit 6 (Week 8) only.
- ¹⁴ Collection is ongoing.

	STATISTICAL ANALYSIS PLAN, Final v1.0
Protocol Number CP543.2003	Sponsor: Concert Pharmaceuticals, Inc.

Appendix 2

Output Conventions

TLF will be generated using SAS® and will be displayed on letter size paper with landscape orientation, 1-inch margins, and 9-point Courier New font.

All TLFs will include a header section comprised of the Sponsor's name, the protocol number, the delivery description, the data cut-off date (if applicable), the TLF number, the TLF title, the analysis population, and the page number (Page X of Y). The footer section will include the TLF footnotes, the CRO's name, the date and time of the execution of the program, and the name of the program.

Summary tables and data listings will be summarized by dosing regimen and overall, as appropriate. All data collected per-protocol and all derived variables will be listed.

Mean and median will be displayed to one more decimal place than the original value; SD and CI will be displayed to two more decimal places than the original value; minimum and maximum will keep the same number of decimal places as the original value. If derived parameters are to be summarized, the number of decimals of the derived values is to be chosen on a case-by-case basis, but the rule above applies.

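### By-visit safety means and the hematology line plots can follow a changing set of patients, and off-drug Week 28 is not separated from the on-treatment visits

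*SAP*

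**What the plan says.** SAP 13.2 (laboratory), 13.3 (vital signs) and 13.5 (ECG) give descriptive statistics by regimen at Baseline and at all later visits, for the value and for its change from Baseline. For hemoglobin, neutrophils, platelets and reticulocytes, 13.2 adds: "Line plots of means (+/- SEM) in laboratory value over time by dosing regimen will be presented for each hematology parameter of interest". The plots show the laboratory value, not its change. The visits to be plotted are not listed.

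Four rules decide who is in each row:

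- SAP 5.3, for scheduled visits: "all data will appear in summary tables based on the nominal timepoint". An unscheduled or repeat result moves to the closest earlier visit and is used only if the scheduled result there is missing.
- SAP 5.4: "Early termination visit assessments will be summarized as a separate visit".
- SAP 6.3: "All other missing efficacy data as well as missing safety data will not be imputed". Missing SALT scores, by contrast, are carried forward or interpolated.
- SAP 3.3: withdrawn patients are not replaced.

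On Week 28 (Visit 11), footnote 4 of the schedule in SAP Appendix 1 says: "The Safety Follow-Up Visit is intended for those patients who do not roll over into an open-label extension and for patients who have been discontinued". Hematology, chemistry, lipids, vital signs and ECG are all scheduled then. Footnote 8, on laboratory sampling, reads: "When possible, collect pre-dose, except on Visit 11". The Protocol synopsis gives the limit on dosing: "Patients will receive up to 24 weeks of study drug".

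Protocol 8.2 and its Table 3 set dose-interruption thresholds for neutrophils, hemoglobin and platelets. An interruption of more than 21 days in a row leads to discontinuation from the study.

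**The concern.** A reader takes a line of means over time to show the same patients changing. Here the set of patients can change from point to point. Three of the four plotted parameters also carry an interruption rule that can end in discontinuation, so leaving can depend on the quantity plotted. If the patients with the largest falls leave, the later points recover without any patient recovering. If one regimen loses more such patients than the other, the two lines can look more alike than the regimens are.

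Week 28 adds a second change. It holds a smaller, selected group, and drug status changes at the same time. A step between Week 24 and Week 28 cannot be read as either recovery or worsening.

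This matters because the comparison of tolerability is part of the primary objective, and these four parameters are the ones the SAP singles out.

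**Working it through.** **Plan figures.** No stated figure is in dispute. The inputs taken from the documents are about 30 patients enrolled and 25 completers per arm (Protocol synopsis and 11.1; SAP 3.1 and 6.1). No dropout rate is given. The two numbers imply a loss of 30 − 25 = 5 per arm, or 5/30 = 16.7%.

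**Who is in each row.** Under the rules above, a patient who stops between Weeks 8 and 12 is in the rows up to Week 8 and in the early-termination row. That patient is absent from Weeks 12 to 24 and returns at Visit 11 unless that visit is waived (Protocol 7.3.1 allows this case by case). A confirmatory low value drawn at an unscheduled visit is left out of the by-visit mean if the visit it is assigned to already has a scheduled result.

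**Shift of the Week 24 mean.** Let d be the fraction lost and Δ the mean of stayers minus the mean of leavers, in SD units. The all-patient mean is (1 − d)·m_stay + d·m_leave. The plotted mean is m_stay. The difference is d·Δ. The standard error of the plotted mean is 1/√n SD. The documents give no Δ, so 0 to 2 SD is an assumed range.

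| Lost of 30 | Δ = 0 | Δ = 0.5 | Δ = 1 | Δ = 2 | SEM at Week 24 |
|---|---|---|---|---|---|
| 2 | 0 | 0.03 | 0.07 | 0.13 | 1/√28 = 0.19 |
| 5 | 0 | 0.08 | 0.17 | 0.33 | 1/√25 = 0.20 |
| 8 | 0 | 0.13 | 0.27 | 0.53 | 1/√22 = 0.21 |

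At 5 of 30, the shift passes one SEM when Δ exceeds 0.20/(5/30) = 1.2 SD.

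Two simulations of 5 lost from 30 bracket the mechanism. If the 5 lost are the lowest on their value plus independent noise of equal SD, the mean shift is 0.20 SD, about one SEM. If the 5 are lost at random, the mean shift is 0, with a chance SD of 0.08.

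**Change from Baseline.** When each patient is compared with his or her own Baseline, losing patients who had a different Baseline level causes no shift. Selection on the change itself remains. The tables give change from Baseline, but the plots do not.

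**Week 28.** The roll-over rate is not stated, so 50%, 80% and 95% are assumed. Completers attending are 25·(1 − r), plus 0 to 5 early stoppers.

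| Roll-over r | Completers | With 5 stoppers | Stoppers' share | SEM with 0 / 5 stoppers (SD) |
|---|---|---|---|---|
| 50% | 12.5 | 17.5 | 29% | 0.28 / 0.24 |
| 80% | 5 | 10 | 50% | 0.45 / 0.32 |
| 95% | 1.25 | 6.25 | 80% | 0.89 / 0.40 |

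Week 28 thus rests on roughly 1 to 18 patients per arm, against 25 at Week 24, and none of them is on drug. Under nominal-visit handling, an early stopper's Visit 11 result may also be labelled Week 28 although it was taken earlier.

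**The case against.** Observed-case summaries by visit are a common descriptive choice, and SAP 13 plans no inference on safety. Cytopenia is also captured elsewhere:

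- Grade 3 or 4 laboratory values arising at any point on treatment (13.2);
- adverse events leading to interruption or discontinuation (13.1);
- reasons for discontinuation by regimen (7.1);
- shift tables to the worst result, promised in 3.4;
- n and change from Baseline in the tables (6.2, 13.2, 13.3, 13.5).

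Much of this stands, and it makes the point one of presentation. It does not settle it. The Grade 3 or 4 counts miss smaller falls, 13.2 does not describe the shift tables that 3.4 refers to it, and no n is required on the plots.

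A reader might infer more than the documents support:

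- *That the trend must move.* Only the patient set must change when someone stops. The mean moves only if leavers differ from stayers.
- *That later means cover only patients who tolerated the drug.* Protocol 8.2 lets patients who recover within the 21-day limit stay in the study, so their values remain in the scheduled rows.
- *That Week 28 is on the plots.* SAP 13.2 does not say, and SAP 5 leaves figure layouts to a separate document.
- *That a regimen difference will be hidden.* Suppose hemoglobin changes by −0.3 g/dL in stayers and −1.8 g/dL in stoppers, with 2 stoppers in one arm and 8 in the other. The all-patient means are (28 × −0.3 + 2 × −1.8)/30 = −0.40 and (22 × −0.3 + 8 × −1.8)/30 = −0.70, while both Week 24 means are −0.30. The arithmetic is right, but every input is assumed. Eight exceeds the implied loss of 5, and Protocol 4.2 reports no hematologic interruptions so far at 12 mg BID. It is a stress case. On the other side, the CTP-543 data that the Protocol describes for 24 mg QD are 7 days in healthy volunteers (4.4.1), so unequal loss cannot be excluded.
- *That Week 28 would show an apparent worsening.* With 5 completers and 5 stoppers at those same values, the Week 28 mean is (5 × −0.3 + 5 × −1.8)/10 = −1.05. That requires all 5 stoppers to attend and none to recover off drug.

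**Conclusion.** The point holds in a limited form. The patients behind the by-visit safety means can change over time, and for hematology the Protocol's own rules can tie exit to the plotted value. At the implied loss of 5 of 30, the Week 24 mean shifts by 0 to 0.33 SD for gaps of 0 to 2 SD. This is below one SEM unless the gap exceeds about 1.2 SD, and zero in expectation if loss is unrelated to the value. The gap is assumed and the loss is inferred from the planned numbers.

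Week 28 is the stronger part, because both the patients and their drug status change and no text separates it from the on-treatment rows. Its size depends on a roll-over rate that the documents do not give.

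For vital signs and ECG, the Week 28 part applies, but the documents contain no exit rule tied to those measurements. No stated figure is wrong and the efficacy analysis is unaffected.

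**What to change.** Change SAP 13.2 for hematology, and apply (b) and (c) in 13.3 and 13.5 for consistency:

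(a) Limit the hematology line plots to Baseline through Week 24, with n printed at each point.

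(b) Add a *last on-treatment value* row, giving value and change from Baseline, for each Safety-population patient with a post-Baseline value. Define it as the last value on or before the last dose, including unscheduled draws. Use the early-termination value only if it meets that definition. Protocol 7.3.1 foresees dosing that ended before that visit, and under 8.2 it may follow an interruption of 21 days or more, so it is not always on treatment.

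(c) Label Week 28 as off-treatment follow-up, show it apart from the on-treatment rows, and keep it off the plots. With so few patients expected, a further paired or split analysis of Week 28 is not needed.

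This needs SAP wording and programming only, with no new data and no change to clinical rules. The downside is slightly longer safety tables.
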